10 STUDY PROCEDURES

10.1 VISIT SCHEDULE

The LTS12551 study consists of 3 periods:

- **Enrollment period:** Combined V1/V2 Visit: Eligible patients from PDY14192, EFC13579 and EFC13691 studies should rollover into LTS12551 the same day as *the end-of-treatment visit of the parent study*.
 - **Note:** A screening period of 0 to 3 weeks was proposed only for patients rolling over from DRI12544. Enrollment from study DRI12544 is complete, thus the screening period does not apply anymore.
- **Treatment period:** Open-label treatment for 48 weeks (1 year) for patients enrolled after approval of Amendment 04 or 96 weeks (2 years) for patients enrolled prior to Amendment 04 approval.

During the open-label treatment period, patients will continue their background therapy dose regimen, as maintained in the parent study or as modified based on Investigator's judgment.

- **Post-treatment period:** 12 weeks.

The study visits should be performed on the planned dates (relative to the first injection) and be adhered to within the ± 3 day visit window with the first 12 weeks and ± 1 week for the remaining study period. Monthly telephone contact should be done with patient after Week 24 to collect safety information.

It is preferred that all study visits take place in the morning. The results of the evaluation will be recorded on the appropriate e-CRF pages. Prior to all screening assessments, after discussion of participation in the study, the written consent form must be signed and dated.

If a patient is prematurely discontinued from treatment, EOT should be scheduled and all assessments planned at the EOT Visit should be performed.

10.1.1 For patients enrolled prior to Amendment 04

The visit schedule for patients enrolled prior to Amendment 04 are shown in the study flowchart in [Section 1.2](#).

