2	23-Nov-2016	Protocol amendment 4 reduces the frequency of assessments for the ACQ-5, AQLQ, clinical laboratories, ECG and ADA variables for all patients in the LTS12551 study.	The scheduled visits and corresponding analysis windows for the endpoints of ACQ-5, AQLQ, clinical laboratories, ECG and ADA are adjusted accordingly per the reduced scheduled visits in the protocol amendment 4.
2	23-Nov-2016	The patient population from study EFC13691 is expected to be different from the	All the planned analyses in LTS12551 study will be performed and presented separately for the

Statistical Analysis Plan SAR231893-LTS12551 - dupilumab

SAP	Data		
number	approved	Rationale	Description of statistical changes
		patient population from the DRI12544, EFC13579 or PDY14192 studies. The patients from EFC13691 are more severe at the baseline of the parent study and are using a different background controller medication, and thus potentially have different safety profiles in general from the patient population from the other parent studies.	patients from EFC13691 study and the patients from DRI12544, EFC13579 or PDY14192 studies, except for the endpoints that are particularly collected for the patients from EFC13691 study only.
3	This version	The layouts of all outputs are changed to avoid potential confounding introduced by between-study variation.	The treatment category (Naïve, Re- treated, Interrupted treatment, and Continuously treated) is removed.
			The layouts of all outputs are changed to:
			For the patients from EFC13691 study, results of each planned analysis will be presented by "Placebo/Dupilumab, Dupilumab/Dupilumab, and All" (see Section 2.3.2).
			For the patients from DRI12544/EFC13579/PDY14192 studies, results of each planned analysis will be presented by the parent study and "All", and by "Placebo/Dupilumab and Dupilumab/Dupilumab" within each parent study (see Section 2.3.2).
3	This version	To be consistent with ISS SAP	The definition of AESI and other selected AE groupings are updated in Section 2.1.4.1

Property of the Sanofi Group - strictly confidential

Page 15

SAP version	Date		
number	approved	Rationale	Description of statistical changes
3	This version	To be consistent with ISS SAP by including the combined PCSA criteria for adult and adolescents	PCSA criteria in Appendix A are updated

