2.4.4 Analyses of efficacy endpoints

There will be no confirmatory analysis for the efficacy variables. All analyses will be done descriptively on the safety population in observed case, as appropriate. The baseline value for efficacy parameters is the original baselines from the parent studies.

For severe exacerbation events, the number of patients with one or more severe exacerbation events (number and qualitative variable: Yes/No), number of severe exacerbation events (qualitative variable: 0, 1, 2, 3, \geq 4), total number of severe exacerbation events, total patient-years, unadjusted annualized severe exacerbation event rate, and individual patient annualized severe exacerbation event rate (number, mean, SD, median, minimum, maximum) will be presented by the treatment category and overall (see Section 2.3.2) during the treatment period. Number and annualized rate will also be analyzed for severe exacerbation with use of systemic corticosteroids for \geq 3 days only, and that with hospitalization or with emergency room visit only. The mean duration of a severe exacerbation will also be summarized.

For the continuous efficacy variables listed in Section 2.1.3, descriptive statistics (mean, SD, median, minimum and maximum) will be presented for the parameter and its change from baseline over visits and by the treatment category and overall (see Section 2.3.2). In addition, figure of mean change from baseline (with corresponding standard error) will be presented for the continuous efficacy parameter over visits and by the treatment category and overall (see Section 2.3.2).

For the categorical efficacy variables listed in Section 2.1.3, the number and percentage will be presented over time for all patients who have data available at that time point by the treatment category and overall (see Section 2.3.2).

In addition, particularly for the patients coming from the EFC13691 study, the descriptive statistics (mean, SD, median, minimum and maximum) for the percentage change from baseline in oral corticosteroids (OCS) dose will be presented over time by the treatment category and overall (see Section 2.3.2); and, the proportion of patients achieving a reduction of 50% or greater in their OCS dose compared with the original baseline in parent study, and the proportion of patients whose background OCS are completely tapered off will be presented over time by the treatment category and overall (see Section 2.3.2).

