10	20	141	127	154						
11	24	169	155	210	After 1st IMP dose date/time	252	127	252	127	252
12	36	253	211	294						
13	48	337	295	378	253	504	253	420	253	420
14	60	421	379	462						
15	72	505	463	546			421	546	421	588
16	84	589	547	630			547	630		
17 (EOT)	96	673	631	d*	505	d*	631	d*	589	d*
18 (EOS)	108	757	d*+1		d*+1		d*+1		d*+1	

Table 5 - Time window for safety variables

*Note: d= max (last IMP dose +14 days, EOT date)

Statistical Analysis Plan SAR231893-LTS12551 - dupilumab

20-Jul-2017 Version number: 3

Vicit	Wook	Target day	Pregnar	ncy Test	Serum Immunoglobulin		
VISIL	Week	Taiget day	Minimum days	Maximum days	Minimum days	Maximum days	
1 & 2	0	Derived		Up to 1st IMP dose date/time		Up to 1st IMP dose date/time	
3	2	15					
4	4	29	After 1st IMP dose date/time	35			
5	6	43	36	49			
6	8	57	50	63			
7	10	71	64	77			
8	12	85	78	98			
9	16	113	99	126			
10	20	141	127	154			
11	24	169	155	210	After 1st IMP dose date/time	252	
12	36	253	211	294			
13	48	337	295	378	253	462	
14	60	421	379	462			
15	72	505	463	546			
16	84	589	547	630	463	630	
17 (EOT)	96	673	631	d*	631		
18 (EOS)	108	757	d*+1				

*Note: d= max (last IMP dose +14 days, EOT date)

For the efficacy assessment, the reference date for the derivation of relative days of events or findings will be the day of the first IMP injection in LTS12551 study. And for the endpoints not measured daily, all available values of scheduled measurements will be assigned to the appropriate visit window according to Table 6. In the event of multiple measurements of the same test in the same window, the one closest to the targeted visit date will be used for the by-visit summary. If they are at the same distance to the target day, the latest one will be used. The pre-dose measurements at Week 0 of LTS12551 are defined in the same way as in the paragraph prior to Table 5.

Vioit	Wook	Spirometry		ACQ-5, AQLQ		
		Target day	Minimum days Maximum days		Minimum days	Maximum days
1&2	0	Derived		1 st IMP dose date/time (Day 1)		1 st IMP dose date/time (Day 1)
3	2	15	2	21		
4	4	29	22	42		
5	6	43				
6	8	57	43	70		
7	10	71				
8	12	85	71	126		
9	16	113				
10	20	141				
11	24	169	127	252	2	252
12	36	253				
13	48	337	253	420	253	
14	60	421				
15	72	505	421	546		
16	84	589	547	630		
17 (EOT)	96	673	631	d*		
18 (EOS)	108	757	d*+1			

Table 6 - Time window for efficacy variables

*Note: d= max (last dose +14 days, EOT date)

Visit Week Target day		EQ-5D, R	esource Utilization	Prescribed	Prescribed OCS dose		

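### SAP Table 6 reports ACQ-5 and AQLQ scores from early end-of-treatment visits in the 48-week cohort as Week 24 or Week 48 results

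*SAP*

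**What the plan says.** SAP 2.5.4 counts days from the first injection in this study. For efficacy endpoints not measured daily, "all available values of scheduled measurements will be assigned to the appropriate visit window according to Table 6". If a window holds several values, "In the event of multiple measurements of the same test in the same window, the one closest to the targeted visit date will be used", and a tie goes to the later value.

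The relevant rows of Table 6 give, in order, visit, week, target day, spirometry minimum and maximum, then ACQ-5/AQLQ minimum and maximum:

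- Week 24: "11 24 169 127 252 2 252"
- Week 48: "13 48 337 253 420 253", with the last maximum blank.

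These are the only post-dose ACQ-5/AQLQ windows. Spirometry also has an EOT row ending at d* and an EOS row starting the day after, where d is the later of last dose plus 14 days and the EOT date.

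On premature discontinuation, Protocol 10.1 says that "EOT should be scheduled and all assessments planned at the EOT Visit should be performed". For patients enrolled after Amendment 04, the EOT visit includes ACQ-5 and AQLQ(S) (Protocol 1.3 and 10.1.2.12). For patients enrolled before it, the EOT visit does not (Protocol 1.2 and 10.1.1.16). Neither cohort has them at EOS.

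On method, SAP 2.4.4 says: "All analyses will be done descriptively on the safety population in observed case, as appropriate".

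**The concern.** A by-visit, observed-case summary is read as the state of patients near the named visit. Here the Week 24 window opens on Day 2, so a score taken two weeks after a single dose can stand as a Week 24 result. The closest-to-target rule cannot help when that is the patient's only post-dose score.

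ACQ-5 and AQLQ are among the key efficacy variables chosen for subgroup analysis (SAP 2.4.4.1), and their by-visit responder rates use the same windows. People who stop early may differ from those who continue. In the Placebo/Dupilumab category, a Day 15 score reflects about two weeks on active drug. FEV1 and ACQ-5 at Week 24 would also cover different patients and different times in one report.

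**Working it through.** **1. Reproducing the window limits.** Target day = 7 × week + 1.

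- Week 12: 7 × 12 + 1 = 85
- Week 24: 7 × 24 + 1 = 169
- Week 48: 7 × 48 + 1 = 337
- Week 72: 7 × 72 + 1 = 505

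Midpoints:

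- (169 + 337)/2 = 253, which gives the 252/253 boundary.
- (85 + 169)/2 = 127, the spirometry Week 24 minimum.
- (337 + 505)/2 = 421, so spirometry Week 48 ends on Day 420.

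The limits therefore fit a midpoint rule, which the SAP does not state. ACQ-5/AQLQ has no earlier or later post-dose visit, so its first window opens after Day 1 and its last is left open.

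**2. Widths.**

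| Window | ACQ-5/AQLQ | Spirometry |
|---|---|---|
| Week 24, length | 252 − 2 + 1 = 251 days | 252 − 127 + 1 = 126 days |
| Week 24, days before / after target | 167 / 83 | 42 / 83 |
| Week 48, days before / after target | 84 / no limit | 84 / 83 |

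**3. Where an early EOT score goes in the 48-week cohort.** Inputs: dosing every 2 weeks with last dose at Week 0, 2, …, 46; EOT 2 weeks after last dose (Protocol 10.1.2.12); a Week 24 score on Day 169 if EOT falls later. That gives 24 possible EOT visits. Week 24 and Week 48 themselves are on target. The other 22 are:

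| EOT at | Days | Visits | Reported as | Days early |
|---|---|---|---|---|
| Weeks 2–22 | 15–155 | 11 | Week 24 | 169 − 15 = 154 down to 169 − 155 = 14 |
| Weeks 26–34 | 183–239 | 5 | Not used; the Day 169 score is closer | – |
| Weeks 36–46 | 253–323 | 6 | Week 48 | 337 − 253 = 84 down to 337 − 323 = 14 |

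**4. The same list under the spirometry limits.** Only EOT at Weeks 18, 20 and 22 (Days 127, 141, 155) is still reported as Week 24. The other 8 (Weeks 2–16, Days 15–113) fall outside. The 6 visits reported as Week 48 do not change.

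**5. Late scores.** A score at Week 72, 84 or 96 (Days 505, 589, 673) would lie 168, 252 or 336 days past the Week 48 target and still inside the open window. The current schedule plans no ACQ-5/AQLQ at those visits or at EOS. Two routes remain, each only if no nearer score exists: a delayed EOT visit in the 48-week cohort, or data from the schedule before Amendment 04, which "reduces the frequency of assessments for the ACQ-5, AQLQ, clinical laboratories, ECG and ADA variables".

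**6. Effect on a summary.** If a share p of the Week 24 scores are early EOT scores and their mean differs from the rest by δ, the Week 24 mean moves by p × δ, and a responder rate moves by at most p. Neither p nor δ is in the documents. For illustration only, with p assumed to be 3% to 8% and δ set at the ACQ-5 minimal important difference of 0.5, the mean moves by 0.03 × 0.5 = 0.015 to 0.08 × 0.5 = 0.04 points, and a responder rate by at most 3 to 8 percentage points.

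**The case against.** The best defence is that this is house convention. Other assessments with few visits are windowed in the same way: ECG and serum immunoglobulin open their Week 24 window after the first dose, and the last windows for immunoglobulin and total IgE are also blank. Spirometry starts its Week 24 window later because it has visits at Weeks 2, 4, 8 and 12. This explains the table, but it does not make a Day 15 score Week 24 data. ECG, moreover, has EOT and EOS rows and a d* limit that ACQ-5/AQLQ lacks.

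It is also fair that each score is used once and nothing is copied to a later visit, so this is mislabelling and not last observation carried forward. Patients with an on-time score keep it. And "There will be no confirmatory analysis for the efficacy variables".

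Three stronger readings are tempting but unsupported:

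- *Off-drug or late scores are routinely reported as Week 48.* No such score is scheduled, so this is only conditional. One caveat: Protocol 10.3.4 refers both to follow-up until the scheduled completion date and to EOT then EOS after 12 weeks. These need reconciling, because the first reading could yield off-drug Week 24 or Week 48 scores.
- *A lone Week 4 score from before Amendment 04 becomes Week 24.* SAP 1.6 says only that the frequency was reduced. The old visit list is not shown.
- *A count from applying a drop-out rate to all 2930 patients.* The EOT questionnaires belong to the 48-week cohort. Removing the 776 DRI12544 patients, whose enrollment was already complete, leaves 2930 − 776 = 2154. That still includes patients from the other parent studies who enrolled before the amendment, and the protocol expects only about 2206 in total.

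**Conclusion.** The point holds for early stoppers in the 48-week cohort. Their EOT scores from about Day 15 to Day 155 are summarised as Week 24 when no on-time score exists, 14 to 154 days early, and those from Day 253 as Week 48, up to 84 days early. The open end and missing d* cut-off at Week 48 are a secondary gap that matters only when no nearer score exists.

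This rests on three assumptions: an early EOT visit counts as a scheduled measurement; EOT falls about 2 weeks after the last dose; and the blank Week 48 maximum is intended and not lost in reading the table. The Week 24 result does not depend on the third.

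The number of patients affected cannot be derived from the documents. The consequence is confined to secondary, descriptive by-visit means and responder rates. The table should be corrected, but no primary conclusion depends on it.

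**What to change.** In Table 6, give ACQ-5/AQLQ the limits already used for spirometry: Week 24 = Days 127–252 and Week 48 = Days 253–420, with scores on or before d*. Add an EOT/early-discontinuation row that summarises early-EOT scores outside these limits. Without that row, patients stopping before Day 127 would drop out of every by-visit ACQ-5/AQLQ summary.

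This is an edit to one table and needs no new data. The cost is a smaller n at Week 24. The fix is not complete: EOT scores from Days 127–155 and 253–323 would still carry the visit label, as they already do for spirometry. The d* limit cannot exclude an EOT score, because d is never earlier than the EOT date; a late EOT score is excluded by the Day 420 limit.

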2.5.5 Unscheduled visits

Unscheduled visit measurements of laboratory data, vital signs, and ECG will be included in the by-visit summaries and figures, as well as the computation of baseline, worst values, and PCSAs.

2.5.6 Pooling of centers for statistical analyses

Not applicable

2.5.7 Statistical technical issues

None

3 INTERIM ANALYSIS

This is an open-label extension study. Interim analyses/reports may be prepared to support regulatory submission of an indication in the dupilumab project or other purpose.

Interim analysis for non-asthma submission

In general, the analyses for this report will focus on the safety evaluations on the accumulative data in LTS12551 as of the cut-off date. Specifically, the report shall include all safety analyses, demographics, baseline characteristics, patient disposition, exposure to IMP, as well as the prior and concomitant medications.

Interim analysis for asthma submission

All planned analyses in this SAP shall be performed for this report.

4 DATABASE LOCK

At the time of the initial dupilumab marketing authorization application for the treatment of Asthma, an interim database lock will be performed. Additional database snapshots may be performed to support regulatory submission of an indication in dupilumab project, or prior to subsequent marketing authorization applications in major markets, eg, EU. The final database lock is planned to occur 4 weeks after last patient last visit.

7 LIST OF APPENDICES

Appendix A:	Potentially clinically significant abnormalities (PCSA) criteria					
Appendix B:	Summary of statistical analyses					
Appendix C:	Low, medium and high dose inhaled corticosteroids- Adults and adolescents (≥ 12 years)					
Appendix D:	Definition of Anaphylaxis					
Appendix E:	List of opportunistic infections					
Appendix F:	Asthma Control Questionnaire, 5-question Version					
Appendix G:	Asthma Quality of Life Questionnaire					
Appendix H:	EuroQol Questionnaire (EQ-5D-3L)					
Appendix I:	SAS code for EQ-5D index utility scoring					

Appendix A Potentially clinically significant abnormality criteria for included laboratory parameters: Combined Adult (≥ 18) and Adolescent (≥ 12 to < 18) criteria abstracted from BTD-009536 V3.0 with approved modifications

Where adolescent criteria (age \geq 12 to <18) are different than adult criteria (\geq 18), the adolescent criteria are provided in parentheses in the combined column.

Parameter	Adults (≥ 18)	Adolescents (≥12 to <18)	Combined
Vitals			
SBP (mmHg)	≤95 mmHg and decrease from baseline ≥20mmHg≥160 mmHg and increase from baseline ≥20 mmHg	≤90 mmHg and decrease from baseline ≥20 mmHg ≥119mmHg and increase from baseline ≥20 mmHg	≤95 (≤90) mmHg and decrease from baseline ≥20 mmHg≥160 (≥119) mmHg and increase from baseline ≥20 mmHg
DBP (mmHg)	≤45 mmHg and decrease from baseline ≥10 mmHg≥110 mmHg and increase	≤54 mmHg and decrease from baseline ≥10 mmHg≥78mHg and increase from	\leq 45 (\leq 54) mmHg and decrease from baseline \geq 10 mmHg
	from baseline ≥10 mmHg	baseline ≥10 mmHg	\geq 110 (\geq 78) mmHg and increase from baseline \geq 10 mmHg
HR (bpm)	≤50 bpm and decrease from baseline ≥20 bpm	NONE	≤50 bpm and decrease from baseline ≥20 bpm
	≥120 bpm and increase from baseline≥20 bpm		≥120 bpm and increase from baseline ≥20 bpm
Respiratory rate	NONE	<12 breaths/min	<12 breaths/min
(breaths/min)		>20 breaths/min	>20 breaths/min
Temperature (°C)	NONE	Rectal, ear or temporal artery: ≥100.4°F/38.0 °C	\geq 38.0 °C rectal/ear/temporal
		Oral or pacifier: ≥99.5 °F/37.5 °C	\geq 37.2 °C axillary
		Axillary or skin infrared: ≥99°F/37.2 °C	
Weight (kg)	≥5% increase from baseline	\geq 5% weight loss from baseline	≥5% increase from baseline (adults only)

Parameter	Adults (≥ 18)	Adolescents (≥12 to <18)	Combined	
	≥5% decrease from baseline		\geq 5% decrease from baseline	
ECG				
Heart rate (bpm)	<50 bpm	≤50 bpm and decrease from baseline >20 bpm	<50 bpm	
(0,)	<50 bpm and decrease from baseline ≥20 bpm	\geq 120 bpm and increase from	<50 bpm and decrease from baseline ≥20 bpm	
	<40 bpm	basenne ≥20 opm	<40 bpm	
	<40 bpm and decrease from baseline ≥20 bpm		<40 bpm and decrease from baseline ≥20 bpm	
	<30 bpm		<30 bpm	
	<30 bpm and decrease from baseline ≥20 bpm		<30 bpm and decrease from baseline ≥20 bpm	
	>90 bpm		>90 bpm	
	>90 bpm and increase from baseline ≥20bpm		>90 bpm and increase from baseline ≥20 bpm	
	>100 bpm		>100 bpm	
	>100 bpm and increase from baseline ≥20bpm		>100 bpm and increase from baseline ≥20 bpm	
	>120 bpm		>120 bpm	
	>120 bpm and increase from baseline ≥20 bpm		>120 bpm and increase from baseline ≥20 bpm	
PR interval	>200 ms	≥180 ms	>200 (≥180) ms	
(ms)	>200 ms and increase from baseline ≥25%		>200 (≥180) ms and increase from baseline ≥25%	
	> 220 ms		>220 ms	
	>220 ms and increase from baseline ≥25%		>220 ms and increase from baseline ≥25%	
	> 240 ms		>240 ms	
	> 240 ms and increase from		>240 ms and increase from	
Parameter	Adults (> 18)	Adolescents (>12 to <18)	Combined	
---------------------	---	--	--	--
	baseline >25%		baseline >25%	
QRS interval (ms)	>110 ms	≥110 ms	>110 ms	
	from baseline ≥25%		baseline ≥25%	
	>120 ms		>120 ms	
	>120 ms and increase from baseline ≥25%		>120 ms and increase from baseline ≥25%	
QT interval (ms)	>500 ms	NONE	>500 ms	
QTc (ms)	>450 ms	Borderline: 431-450 ms (Boys); 451-470 ms (Girls)	Borderline: 451- 480 ms (431- 450 ms boys; 451- 470	
	>480 ms	Prolonged*: >450 ms (Boys); >470 ms (Girls)	Prolonged: >480 ms (>450	
		Additional: ≥500 ms	$\frac{\text{ms boys; >470 ms girls)}}{\text{Additional: > 500 ms}}$	
	AND			
	Increase from baseline]30- 60] ms	AND	AND	
	Increase from baseline >60 ms	Borderline: Increase from baseline 30-60 ms	>30 to ≤60 ms increase from baseline	
		Prolonged*: Increase from baseline >60 ms	>60 ms increase from baseline	
Hematology				
Hemoglobin (g/L)	≤115 g/L (Male); ≤95 g/L (Female)	<6.2 mmol/L or 10 g/dL or any decrease \geq 1.2 mmol/L or 2 g/dL	Decrease from baseline ≥ 20 g/L	
	≥185 g/L (Male); ≥165 g/L (Female)		≤115 g/L males; ≤95 g/L females (<100 g/L adolescents)	
	≥20 g/L		\geq 185 g/L males; \geq 165 g/L females (\geq 185 g/L adolescents)	
Hematocrit	≤0.37 v/v (Male) ; ≤0.32	<0.32 1/1 or 32 %	$\leq 0.37 \text{ v/v males;} \leq 0.32 \text{ v/v}$	

Parameter	Adults (> 18)	Adolescents (>12 to <18)	Combined
(v/v)	v/v (Female)		females (<0.32 v/v)
	≥0.55 v/v (Male) ; ≥0.5 v/v (Female)	>0.47 l/l or 47 %	≥0.55 v/v males; ≥0.5 v/v females (>0.47 v/v)
RBC (Tera/L)	≥6 Tera/L	NONE	≥6 Tera/L
Platelets (Giga/L)	<100 Giga/L ≥700 Giga/L	<100 GIGA/L or 100,000 /mm3 >700 GIGA/L or 700,000 /mm3	<100 Giga/L ≥700 Giga/L
WBC (Giga/L)	<3.0 Giga/L (Non-Black); <2.0 Giga/L (Black) ≥16.0 Giga/L	<4,5 GIGA/L or 5,000 /mm3 >13.5 GIGA/L or 17,000 /mm3	<3.0 Giga/L non-Black; <2.0 Giga/L Black (<4.5 Giga/L) ≥16 (>13.5) Giga/L
Lymphocytes (Giga/L)	>4.0 Giga/L	<0.6 GIGA/L or 600 /mm3 >6.0 GIGA/L or 6,000 /mm3	<0.6 Giga/L (adolescents only) >4.0 (>6.0) Giga/L
Neutrophils (Giga/L)	<1.5 Giga/L (Non- Black);<1.0 Giga/L (Black)	<1.2 GIGA/L or 1,200 /mm3 > 1 ULN	<1.5 Giga/L non-Black; <1.0 Giga/L Black (<1.2 Giga/L) >1xULN (adolescents only)
Monocytes (Giga/L)	>0.7 Giga/L	NONE	>0.7 Giga/L (adults only)
Basophils (Giga/L)	>0.1 Giga/L	NONE	>0.1 Giga/L (adults only)
Eosinophils (Giga/L)	>0.5 Giga/L or >ULN (if ULN≥0.5 Giga/L)	>0.5 GIGA/L or 500 /mm3 Or >ULN if ULN >0.5 GIGA/L or 500/mm3	>0.5 Giga/L or > ULN if ULN >0.5 Giga/L
Clinical Chemistry			
Glucose (mmol/L)	≤3.9 mmol/L and <lln ≥11.1 mmol/L (unfasted); ≥7 mmol/L (fasted)</lln 	Hypoglycaemia <2.7 mmol/L Hyperglycaemia ≥7 mmol/L (fasted after >12 hours of fast); ≥10.0 mmol/L (unfasted)	≤3.9 mmol/L and < LLN (<2.7 mmol/L) ≥11.1 (≥10) mmol/L unfasted; ≥7 mmol/L fasted
Glucose (mg/dL)	NONE	Hypoglycaemia <50 mg/dL	\leq 70 mg/dL and < LLN (<50 mg/dL)

Parameter	Adults (≥ 18)	Adolescents (≥12 to <18)	Combined
		Hyperglycaemia $\geq 120 \text{ mg/dL}$ (fasted after >12 hours of fast); $\geq 180 \text{ mg/dL}$ (unfasted)	≥200 (≥180) mg/dL unfasted; 126 (≥120) mg/dL fasted
Total cholesterol (mmol/L)	≥7.74 mmol/L	≥6.20 mmol/L	≥7.74 (≥6.20) mmol/L
Total cholesterol (mg/dL)	NONE	≥240 mg/dL	≥300 (≥240) mg/dL
Creatine phosphokinase	>3 ULN	≥3 ULN	>3 ULN
(ULN)	>10 ULN		>10 ULN
Albumin (g/L)	≤25 g/L	NONE	$\leq 25 \text{ g/L} (\text{adults only})$
Sodium	\leq 129 mmol/L	\leq 129 mmol/L or 129 mEq/L	\leq 129 mmol/L
(mmol/L)	≥160 mmol/L	≥150 mmol/L or 150 mEq/L	≥160 (≥150) mmol/L
Potassium (mmol/L)	<3 mmol/L	\leq 3.5 mmol/L or 3.5 mEq/L	<3.0 (≤3.5) mmol/L
	≥5.5 mmol/L	\geq 5.5 mmol/L or 5.5 mEq/L	\geq 5.5 mmol/L
Bicarbonate (mmol/L)	NONE	$\leq 16 \text{ mmol/L or } 16 \text{ mEq/L}$	$\leq 16 \text{ mmol/L}$
``´´		\geq 30 mmol/L or 30 mEq/L	≥30 mmol/L
Chloride (mmol/L)	<80 mmol/L	≤80 mmol/L or 80 mEq/L	<80 mmol/L
· · · ·	>115 mmol/L	\geq 115 mmol/L or 115 mEq/L	>115 mmol/L
Creatinine	$\geq 150 \ \mu mol/L \ (Adults)$	$\geq 132 \mu mol/L$	≥150 (≥132) µmol/L
(µmol/L)	\geq 30% change from baseline		\geq 30% change from baseline
	≥100% change from baseline		\geq 100% change from baseline
Creatinine (mg/dL)	NONE	$\geq 1.5 \text{mg/dL}$	≥1.7 (≥1.5) mg/dL
			\geq 30% change from baseline
			$\geq 100\%$ change from baseline
Creatinine clearance	<15 (end stage renal disease)	<15 (end stage renal disease)	<15 mL/min (end stage renal disease)

Parameter	Adults (≥ 18)	Adolescents (≥12 to <18)	Combined
(mL/min)			
	$\geq 15 - \langle 30 \rangle$ (severe decrease	$\geq 15 - \langle 30 \rangle$ (severe decrease in	\geq 15 - <30 mL/min (severe
	In GFR)	GFR)	decrease in GFR)
	\geq 30 - < 60 (moderate decrease in GFR)	\geq 30 - < 60 (moderate decrease in GFR)	≥30 - <60 mL/min (moderate decrease in GFR)
	≥60 - <90 (mild decrease in GFR)	≥60 - <90 (mild decrease in GFR)	≥60 - <90 mL/min (mild decrease in GFR)
	\geq 90 (normal GFR)	\geq 90 (normal GFR)	
BUN (mmol/L)	≥17 mmol/L	≥6.4 mmol/L	≥17 (≥6.4) mmol/L
BUN (mg/dL)	≥48 mg/dL	$\geq 18 \text{ mg/dl}$	≥48 (≥18) mg/dL
Uric acid	<120 µmol/L	≤119 µmol/L	<120 µmol/L
	>408 µmol/L	≥476 µmol/L	>408 (≥476) μmol/L
Uric acid (mg/dL)	NONE	≤2.0 mg/dL	$\leq 2 \text{ mg/dL}$
(\geq 8.0 mg/dL	\geq 7 (\geq 8) mg/dL
ALT (ULN)	>3 ULN	≥3 ULN	>3 ULN
	>5 ULN	≥5 ULN	>5 ULN
	>10 ULN	≥10 ULN	>10 ULN
	>20 ULN	≥20 ULN	>20 ULN
AST (ULN)	>3 ULN	≥3 ULN	>3 ULN
	>5 ULN	≥5 ULN	>5 ULN
	>10 ULN	≥10 ULN	>10 ULN
	>20 ULN	≥20 ULN	>20 ULN
ALP (ULN)	>1.5 ULN	≥1.5 ULN	>1.5 ULN
Total bilirubin	>1.5 ULN	≥1.3 ULN	>1.5 (≥1.3) ULN
	>2 ULN		>2 ULN
ALT and total bilirubin (ULN)	ALT>3 ULN and TBILI>2 ULN	$ALT \ge 3$ ULN and Total Bilirubin ≥ 2 ULN	ALT >3 ULN and TBILI >2 ULN

Parameter	Adults (≥ 18)	Adolescents (≥12 to <18)	Combined
Conjugated and total bilirubin (ULN)	Conjugated Bilirubin >35% Total Bilirubin and TBILI>1.5 ULN	>35% Total Bilirubin and TBILI≥1.3 ULN	Conjugated bilirubin $> 35\%$ total bilirubin and total bilirubin >1.5 (≥ 1.3) ULN

